---------------------------	--

	30.The patient is in a coma.
--	------------------------------

Statistics	
This prospective, multi-center randomized adaptive clinical study is composed of three (3) phases: screening, procedure, and follow-up. The analyses to address the primary and secondary objectives will be based on the data collected during the procedure and follow-up period. There is a single primary effectiveness endpoint and a primary safety endpoint. There are five (5) secondary endpoints that will be evaluated statistically in hierarchical order. The results from the fourteen tertiary endpoints will be summarized and compared between the two (2) randomized treatment arms as supportive information.
 
The non-inferiority margins for the primary and secondary endpoints come from five (5) published reference studies using retrieval devices in a similar subject population. Where a non-inferiority margin is not available from the peer-reviewed literature, the confidence limit of the difference (Envi™-SR minus Control) in the proportion of subjects experiencing the event of interest, establishing non-inferiority will require zero to be contained within the 1-sided 97.5% or 2-sided 95% confidence limits.
 
The target Intention to Treat (ITT) sample size for this clinical investigation is 270 subjects: 135 subjects per arm. An interim assessment based on conditional power (CP) will be performed by the independent Data Monitoring Committee (DMC) after 50% of the target ITT enrollment (135 subjects) has been randomized and either completed the 90-day (<math>\pm 15</math> days) evaluation visit or withdrawn prematurely. The interim assessment may result in the target enrollment being increased to a maximum of 560 subjects consented and enrolled. Following the interim assessment, the DMC will provide a non-binding recommendation to the sponsor to either continue enrolling to the target sample size, increase enrollment up to the maximum sample size, or stop the study for futility (<math>CP < 37\%</math>).
 
At the time of the interim assessment performed by the DMC, the Committee will receive data on all adverse events, effectiveness, investigational site, time last seen well (TLSW), and Additional Therapy for each patient. Through inspection of the tabulated data the DMC will be tasked with examining if data are consistent with planning estimates as described in the DMC Charter.
 
The Intention to Treat (ITT) population will include all subjects that have signed the informed consent form (ICF) and were randomized. The primary population for the primary and secondary analyses for this study will be the ITT population. The ITT population will also serve as the Safety population.
 
Randomization to either Envi™-SR or Control will be performed in a 1:1 ratio, stratified by six (6) factors using a dynamic randomization scheme:
 
 
• Age: <math>\geq 67</math> and <math>< 67</math>
 
• Site of occlusion: ICA, MCA M1, MCA M2
 
• Baseline/Enrollment NIHSS score: <math>< 17</math> and <math>\geq 17</math>
 
• Prior IV t-PA usage: Yes and No
 
• Time to symptom onset: <math>\geq 6</math> hours and <math>< 6</math> hours
 
• Baseline ASPECTS: 6-7 and 8-10
 
 
This randomized study will ensure that the assessing clinical team are blinded to treatment assignment. Due to the nature of the treatment, and access to the patient records, the treatment team is not required to be blinded. The treatment team will obtain a randomization assignment using a web-based randomization system.
 
The primary effectiveness and safety endpoints will be evaluated simultaneously. If the primary effectiveness endpoint is met (Envi™-SR non-inferior to Control), the secondary effectiveness endpoints will be evaluated statistically in the hierarchical order presented in this protocol and the Statistical Analysis Plan (SAP).

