## 8. Statistical Analysis

### 8.1. Study Design

The Envi™-SR study is a prospective, multi-center randomized adaptive design where the primary effectiveness endpoint will be assessed via a blinded evaluation of the Modified Rankin Scale (mRS). Up to 30 study centers may participate in this study. A pre-specified interim assessment for conditional power (CP) for potential sample size readjustment will be performed by the independent DMC after 50% of the minimum target ITT sample size (270/2: 135 patients) have been randomized and completed the day 90 evaluation or prematurely discontinued from the study. The purpose of this trial is to provide confirmatory clinical evidence that the Envi™-SR Thrombectomy Device provides benefits similar to those of the Control Devices for LVO strokes.

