### 8.2. Sample Size Considerations

The objective of this trial is to demonstrate similar performance after treatment with the Envi™-SR device compared to the expected proportion of good outcomes at 90 days in the Control arm. The expected proportion of good outcomes in the Envi™-SR arm was estimated based on earlier results with Control. A -12.5% non-inferiority margin (NIM) will be used to examine the lower bound of the 1-sided 97.5% exact binomial confidence interval of the difference (Envi™-SR minus Control) in the proportion of patients with a 90-day mRS of 0-2. The null hypothesis and alternative hypothesis are presented below.

Ho: Envi™-SR – Control  $\leq$  -12.5%

Ha: Envi™-SR – Control  $>$  -12.5%

If the lower bound of the 1-sided 97.5% exact binomial confidence interval of the difference (Envi™-SR minus Control) in the proportion of patients with a 90-day mRS of 0-2 is greater than -12.5%, then non-inferiority will be established.

The planning estimates for the Envi™-SR study considered the lower bound of the 2-sided 95% (asymptotic) confidence interval from the SWIFT PRIME study for estimation (50.5%). Sample size estimates were prepared for this parallel design study assuming a non-inferiority margin of -12.5% (Envi™-SR successes [%] minus Control successes [%]). Under the alternative hypothesis, non-inferiority would be claimed if the lower bound of the 1-sided 97.5% confidence interval of the difference is less than the non-inferiority margin of -12.5%. All planning estimates are performed for the ITT population as this is the primary population for analysis.

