### Target Sample Size

Assuming 46% of the Control patients and 50.5% of the Envi™-SR patients have an mRS score

$\leq 2$  at 90 days, 270 total subjects (ITT) will be required.

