### Maximum Sample Size

If the gap narrows between the 2 randomized groups to 49.5% (Control) and 50.5% (Envi™-SR), 426 total patients (ITT) will be required (type 1 error rate of 2.5%, power of 80%). A loss to follow-up rate of 5% or less is expected. Missing data will be imputed as described in section 8.2.2. As multiple imputation could dampen the signal from the subject data that is imputed, an additional 5% of subjects may be added to compensate for any potential impact, leading to a total sample size of 448 subjects (ITT).

All estimates are performed based on the ITT population. However, all enrolled subjects (i.e., consented), including enrolled screen failures, will count toward the maximum sample size of 560 patients. The rate of enrolled screen failures is not expected to exceed 25%. Therefore, the maximum sample size for enrollment will be the ITT maximum sample size plus 25%, or 560 patients.

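### The 80% power in section 8.2 is a fixed-sample figure: it makes no allowance for the interim futility rule at conditional power below 37%, and the conditional power is not defined

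*Combined protocol and SAP*

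**What the plan says.** Section 8.2, Target Sample Size, takes 46% good outcomes on Control and 50.5% on Envi-SR and concludes that "270 total subjects (ITT) will be required". Maximum Sample Size narrows the gap: "If the gap narrows between the 2 randomized groups to 49.5% (Control) and 50.5% (Envi™-SR), 426 total patients (ITT) will be required", with "type 1 error rate of 2.5%, power of 80" per cent. A 5% addition takes 426 to 448 ITT subjects. The test uses "the lower bound of the 1-sided 97.5% exact binomial confidence interval of the difference" against a margin of -12.5 points.

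Section 8.1 describes the interim only as a sample-size step: "A pre-specified interim assessment for conditional power (CP) for potential sample size readjustment will be performed", at half of 270 (135 patients). It gives no futility threshold. The Statistics part of the Protocol Synopsis gives the DMC three options in a non-binding recommendation to the sponsor: continue to target, or "increase enrollment up to the maximum sample size, or stop the study for futility", with futility set at CP below 37%. Neither place says which treatment effect the CP assumes, which final N it is projected to, or what CP range leads to an increase.

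**The concern.** A futility look can only lower power, because some trials that would have succeeded are stopped. If 270 and 426 were sized as though there were no look, the power in section 8.2 belongs to a different design from the one that will be run. A 37% cut is also high enough for the loss to matter under some definitions of CP. The scenario most exposed is 49.5% v 50.5%, the one used to justify the larger sample. At stake is a device that is truly about equal to Control being recommended for abandonment at halfway, by a rule whose cost the sponsor has not seen. With CP undefined, the same interim data could also support opposite recommendations.

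**Working it through.** **Inputs.** From section 8.2: rates 46/50.5 and 49.5/50.5, margin 0.125, one-sided 2.5%, sizes 270, 426 and 448. From 8.1 and the synopsis: 1:1 allocation, look at 135 (67.5 per arm), stop recommendation at CP < 37%. Assumed, because not given: the effect and final N used in CP, and an increase to 448 when CP is 37-80%.

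**The plan's sizes.** With V = pc(1-pc) + pt(1-pt), n per arm = (1.960 + 0.842)² V / (difference + 0.125)².
- 46/50.5: V = 0.2484 + 0.2500 = 0.4984; n = 7.849 × 0.4984 / 0.170² = 135.4, so 136 per arm, 272 in total (plan: 270). Power at 135 per arm: SE = √(0.4984/135) = 0.0608; 0.170/0.0608 = 2.798; Φ(2.798 - 1.960) = 79.9%.
- 49.5/50.5: V = 0.49995; n = 7.849 × 0.49995 / 0.135² = 215.3, so 216 per arm, 432 in total (plan: 426). Power at 213 per arm is 79.6%.

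Both are single-stage sizes, with nothing added for the look.

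**Where 37% falls, CP by current trend projected to 270.** With t = 0.5, CP = Φ[(Z1/√t - 1.96)/√(1-t)]. The 37% quantile is -0.332, so Z1 = (1.960 - 0.332 × 0.707) × 0.707 = 1.220. The interim SE is √(0.4984/67.5) = 0.0859, so the cut is -0.125 + 1.220 × 0.0859 = -0.020.

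**Stop probability** = Φ(1.220 - interim drift), where drift is (true difference + 0.125) divided by the interim SE:
- 46/50.5: Φ(1.220 - 1.978) = 22%
- 49.5/50.5: Φ(1.220 - 1.569) = 36%
- equal devices (50/50): Φ(1.220 - 1.452) = 41%

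**CP by planned effect projected to 270.** CP = Φ[(Z1√t + 2.798(1-t) - 1.96)/√(1-t)]. Setting this to 0.37 gives Z1 = 0.462, a cut of -0.125 + 0.462 × 0.0859 = -0.085. Stop probabilities are Φ(0.462 - 1.978) = 6%, Φ(0.462 - 1.569) = 13% and Φ(0.462 - 1.452) = 16%.

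**Power with the recommendation followed.** This was simulated with independent stage statistics weighted by √n; success means not stopped and final Z > 1.96. The last column sends every unstopped trial to 448.

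| CP definition | Cut (points) | 46/50.5, N = 270 | 46/50.5, increase zone | 49.5/50.5, increase zone | 49.5/50.5, ceiling |
|---|---|---|---|---|---|
| Current trend to 270 | -2.0 | 70% | 74% | 55% | 58% |
| Planned effect to 270 | -8.5 | 78% | 87% | 71% | 75% |

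Current trend projected to 448 lies between these: cut -4.6 points, 79% at 46/50.5 with the increase zone, and at most 66% at 49.5/50.5. Planned-effect CP projected to 448 puts the cut near -26 points, so almost no trial is stopped. Power at 49.5/50.5 then depends on the increase rule and reaches 81.5% if all trials go to 448.

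**Splitting the shortfall at 49.5/50.5 (current trend to 270).** With the same increase zone and no futility stop, power is 65.5%; with the stop it is 55.2%. The futility rule accounts for 65.5 - 55.2 = 10.3 points. The other 80 - 65.5 = 14.5 points arise because only about 23% of trials are increased.

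**The case against.** The strongest reply is that the result depends on a definition not in the text reviewed. The protocol refers to a DMC Charter and an SAP for further detail, and either may define CP and report operating characteristics. The 80% is also attached in the text to a fixed 426; for 270 it is only inferred, from the arithmetic. At the target scenario the loss is not general: under planned-effect CP with the increase included, power is about 87%, above 80%. All of this stands, and it limits the claim. It does not make a single-stage 80% describe the adaptive design.

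A reader might infer several stronger things that the documents do not support:
- That the rule would end the trial at -2 points. The synopsis makes it a non-binding recommendation, and the -2.0 cut needs current-trend CP projected to 270.
- That no route leads simply to 270. Continuing to target is the first option listed; what is missing is the CP value separating it from an increase.
- That the whole gap at 49.5/50.5 is due to futility. More than half comes from the limited increase.
- That 37% is an error and a cut such as 10% should replace it. The threshold trades power against exposure, and section 4 says enrollment should be kept as low as rigorous evaluation allows. With current-trend CP to 270, the 37% rule stops a device truly 12.5 points worse 89% of the time; a 10% cut stops it 77% of the time, for about 16 more expected subjects.
- That type I error is inflated. Futility stopping does not raise it.

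**Conclusion.** The concern holds in this form: the sizes and the 80% in section 8.2 are fixed-sample figures, the text reviewed makes no allowance for the stop recommendation at CP below 37%, and CP is undefined in both effect and final N. The size of the loss depends on that definition. If the recommendation is followed, power at 49.5/50.5 is about 55% (at most 58%) under current-trend CP to 270 and about 71% (at most 75%) under planned-effect CP to 270. At 46/50.5 it runs from 70-74% to about 87%. Under planned-effect CP projected to 448 the futility rule itself costs almost nothing. These figures rest on normal approximations, a look at exactly 135 subjects and, where an increase is included, an assumed 37-80% zone. The stated power needs correcting; the choice of 37% does not, by itself.

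**What to change.** In section 8.2, define CP by its assumed effect and projected N, and give the CP range that leads to an increase and the N it leads to. Make section 8.1 and the synopsis agree, since 8.1 now gives no futility threshold. Replace the fixed-sample 80% with simulated power and stop probabilities for the full design (look, futility rule, increase rule) at 46/50.5 and 49.5/50.5, and say plainly where power falls below 80%. Adding the equal-devices case would show the sponsor the chance of a stop recommendation when the devices do not differ. The sponsor can then keep or lower 37% knowing the trade. The cost is a short simulation, wording changes and, under most definitions, a less favourable stated power at 49.5/50.5.

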## 1. Introduction

In the simplest terms, a stroke is an interruption of blood flow to the arteries in the brain. Sometimes called a “heart attack” of the brain, time to tissue reperfusion is the critical factor for prognosis and final patient outcome. Just like coronary flow interruptions, a stroke may be caused either by a blockage (clot) in the blood vessel (ischemic stroke), or bleeding due to a rupture or perforation of the affected vessel (hemorrhagic stroke).

It is estimated that worldwide, eighty percent of all strokes are ischemic in nature. Acute ischemic stroke (AIS) is considered the first, second or third leading cause of death worldwide. The World Health Organization predicts that disability-life adjusted years (DALYS) from stroke will rise from 38 million in 1990 to over 60 million by the year 2020. Globally up to 15 million people will suffer a stroke, with 5.9 million stroke related deaths and 10.2 million DALYs lost. In Europe, the reported incidence of stroke in men varies from 101.1 to 239.3 per 100,000, to 63.0 to 158.7 per 100,000 in women. Ischemic stroke accounts for the majority of all strokes, among which 8-12% result in death within the first 30 days. In the US, the costs of stroke are estimated by the National Institute of Health to exceed \$73 billion annually. Known risk factors and predictors of stroke include cardiac comorbidities (arrhythmias), chronic hypertension, physical inactivity, larger waist-to-hip ratios, elevated lipid levels, and histories of diabetes, smoking, increased alcohol intake and psychosocial stress and/or depression.

Ischemic strokes contribute to significant morbidity and mortality worldwide, especially in developed countries. More than eight in 10 strokes happen because an artery becomes blocked, causing a sudden loss of blood flow to part of the brain. Damage to brain tissue will occur initially in the region contiguous to the blocked artery (the so-called “*infarct core*”), while a “*penumbra*” of at-risk tissue surrounding this region remains viable for some time following onset of stroke and with timely intervention may respond to efforts to restore blood flow to the region.

Ischemic strokes can be due to large-vessel atherosclerosis, aorto-cardioembolism, small-vessel occlusion, other determined causes, and undetermined causes. Acute ischemic stroke due to large vessel occlusion (LVO)-vertebral, basilar, carotid terminus, middle and anterior cerebral arteries- likely portends a worse prognosis than stroke unassociated with LVO.

The large vessels of the brain include the Internal Carotid Artery (ICA), Middle Cerebral Artery (MCA), Anterior Cerebral Artery (ACA), Vertebral Artery (VA), and the Basilar Artery (BA). Occlusion of these large arteries in ischemic stroke is associated with significant disability and mortality. Revascularization of intracranial arterial occlusions is the therapeutic goal in stroke therapy. Endovascular mechanical revascularization (thrombectomy) is an increasingly used method for intracranial large vessel recanalization in acute stroke. Currently, a number of mechanical recanalization devices are in clinical use. First generation devices included the Merci Retriever device. Second generation devices based on stent-like technology, referred to as “Stentriever®,” “stent-retrievers,” “stent retrievers,” or simply “retrievers” are currently the standard of care for treatment of LVO and acute ischemic stroke in a defined subset of AIS patients.

The Envi™-SR has been developed and CE marked in Europe for revascularization in patients experiencing AIS. The Envi™-SR is approved for use in the US strictly within the confines of the NV-001 Study. In this study the Envi™-SR is intended for use in the neurovasculature per the indications listed below.

1. The Envi™-SR is indicated for use to restore blood flow in the neurovasculature by removing thrombus for the treatment of acute ischemic stroke to reduce disability in patients with a persistent, proximal anterior circulation, large vessel occlusion, and smaller core infarcts who have first received intravenous tissue plasminogen activator (IV t-PA).

Endovascular therapy with the device should be started within 6 hours of symptom onset.

2. The Envi™-SR is intended to restore blood flow in the neurovasculature by removing thrombus in patients experiencing ischemic stroke within 8 hours of symptom onset. Patients who are ineligible for IV t-PA or who fail IV t-PA therapy are candidates for treatment.
3. The Envi™-SR is indicated for use to restore blood flow in the neurovasculature by removing thrombus for the treatment of acute ischemic stroke to reduce disability in patients with a persistent, proximal anterior circulation, large vessel occlusion of the internal carotid artery (ICA) or middle cerebral artery (MCA)-M1 segments with smaller core infarcts (0-50 cc for age < 80 years, 0-20 cc for age ≥ 80 years). Endovascular therapy with the device should start within 6-24 hours of time last seen well in patients who are ineligible for intravenous tissue plasminogen activator (IV t-PA) or who fail IV t-PA therapy.

## **1.1. Background**

### **1.1.1. Intra-Venous and Intra-Arterial Thrombolytics**

Currently, IV lytics are used in Europe and the United States for patients presenting up to 4.5 hours after symptom onset. Although in the US IV tissue plasminogen activator (t-PA) is indicated for use in patients presenting up to 3 hours after symptom onset, US national clinical practice guidelines recommend administering IV lytics in the 3-4.5 hours window to those patients who meet the ECASS 3 study inclusion/exclusion criteria.

In addition to time constraints, IV thrombolytic therapy has been demonstrated to be less effective in recanalizing proximal occlusions of large vessels, such as the ICA and MCA. Since a large percentage of strokes presenting at hospitals are large vessel occlusions, this is an important clinical challenge to address. Additionally, not all patients may be treated with thrombolytic therapy, and so mechanical thrombectomy is a valuable alternative in patients contraindicated for t-PA or where t-PA treatment is not effective.

Direct arterial infusion of thrombolytic agents was first introduced in the late 1990's and has been shown to have moderate recanalization success rates in smaller vessels when administered within 1-4 hours of the event. Intra-arterial infusion of thrombolytic agents is not currently indicated in the US.

### **1.1.2. Bridging Therapy**

Acute stroke treatment protocols vary by hospital center. CT or other imaging is used to exclude hemorrhagic stroke, and CTA (CT Angiography) or MR is used to confirm Large-Vessel Occlusion. Additional imaging assessment, such as use of MRA and/or CT Perfusion, varies by center. Since the presentations of clinical results from the MR CLEAN, ESCAPE, SWIFT PRIME, EXTEND-IA, and REVASCAT studies and ARISE II, many centers have adopted a bridging approach to treatment – immediately starting an IV dose of lytics, then transferring the patient to the angiography suite of a comprehensive stroke center as quickly as possible to speed the time to intra-arterial intervention, if needed. Bridging therapy should occur as determined appropriate by the physician and local practice guidance.

### **1.1.3. Ethical Considerations – Global**

The Envi™-SR device is not cleared in either the U.S. by the FDA or in Canada by Health Canada. It is an investigational device that may be used in the U.S. and Canada within the confines of the NV-001 Study. The purpose of this IDE Study is to gather information on device effectiveness, safety, and performance to support an application for clearance to FDA and Health Canada.

For subjects enrolled in European study sites, the Envi™-SR device will be used according to the investigational indications for use per the instructions for use. It is an investigational device that may be only used within the confines of the NV-001 Study. The collection and analysis of the data requires ethical approval.

The intent of the NV-001 Study is to collect data on subjects in a prospective manner; all subjects who are screened and meet all Inclusion/Exclusion criteria will be included in the analysis. Coded subject data in the form of angiographic and CT and/or MRI images, and completed case report forms are required in order to assess the study endpoints. Informed consent will be sought from the subjects or their legal representative for participation and to give permission for the sponsor and subcontractors (Contract Research Organization (CRO), Clinical Events Committee (CEC), Data Monitoring Committee (DMC), and Core Lab) to have access to these data.

Physicians should follow local practice guidance's, their own routine best practice, requirements per this protocol, and the Envi™-SR or control device's instructions for use, when participating in the study.

